Myelodysplastic syndrome (MDS) and acute myeloid leukemia (AML) are considered adverse events of special interest (AESI), as these events have been observed in patients exposed to cytotoxic chemotherapy (eg, platinum and anthracyclines) used for treatment of ovarian cancer as well as with PARP inhibitors, including rucaparib. Patients in rucaparib clinical studies diagnosed with MDS or AML had significant confounding risk factors including prior cytotoxic chemotherapy, and in some cases a deleterious BRCA mutation, which increases risk for developing cancer(s). Based on these confounding factors, there is insufficient scientific evidence to conclude that MDS and AML are causally related to rucaparib.

Adverse events (AEs) of pneumonitis have been reported with PARP inhibitor treatment, including in clinical trials evaluating rucaparib. Currently, however, there is a lack of understanding of a mechanistic link between pneumonitis and PARP inhibitor treatment, and causality assessment is often confounded by lack of a consistent clinical pattern as well as other pre-disposing factors, such as cancer and/or metastases in lungs, underlying pulmonary disease, smoking history, and/or previous chemotherapy and radiotherapy. pharmaand GmbH (pharma&) is seeking to understand whether or not there is a relationship between pneumonitis and rucaparib treatment; thus, pharma& is designating pneumonitis as an AESI to gather data to enable a thorough evaluation and assessment of the event and associated terms specified in Section 8.7.

More information on AESIs experienced by patients in rucaparib clinical studies is provided in the rucaparib IB.

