7.4.6 Long-term Follow-up (LTFU)

Patients who complete the Safety Follow-up Visit(s) after the last dose of study treatment will continue in long-term follow-up as described below.

- Disease assessment for patients who discontinued treatment for reason other than disease progression or death. Tumor scans should continue to be performed at 12-week intervals (up to 7 days prior permitted) relative to C2D1 for the first 3 years and every 24 weeks thereafter until radiologic disease progression by RECIST v1.1, as assessed by the investigator, is documented;
- CA-125 measurement should be performed at the same time as radiological imaging;
- Subsequent treatments, secondary malignancy monitoring, and OS information will be collected for all patients every 12 weeks (± 14 days) until death, loss to follow-up, withdrawal of consent from study, or closure of the study, starting 12 weeks after SFU1. Follow-up can be performed via the telephone. Diagnosis of any secondary malignancy requires appropriate documentation (ie, laboratory and/or pathology reports) and should be reported as indicated in Section 8.7;
- SAEs assessed as potentially related to study drug, and AESIs of MDS and AML irrespective of causality, are to be reported as specified in Section 8.7;
- SAEs unrelated to IV drug do not need to be captured after the 28-day follow-up visit/period. Only those related or possibly related to IV drug should be captured until the 5-month SFU2.

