7.5.4 Safety Evaluations

7.5.4.1 Adverse Event Assessment

The investigator has the responsibility for assessing the safety of the patients and for compliance with the protocol to ensure study integrity. During the screening period, unless otherwise required by local regulations, SAEs which are related to protocol-mandated assessments will be reported. Once enrolled and study drug is administered, patients will be monitored for all AEs/SAEs/AESIs during study participation and until 28 days after the last dose of oral study drug and 5 months after the last dose of IV study drug, whichever occurs

later. After the 28-day (oral) or 5-month (IV) window, only SAEs assessed as potentially related to study drug (including serious reports of pneumonitis or similar events, ie, interstitial lung disease, pulmonary fibrosis, acute interstitial pneumonitis, alveolitis necrotizing, alveolitis, hypersensitivity pneumonitis, and organizing pneumonia, if considered to be related to study drug), and AESIs of MDS and AML irrespective of causality, need to be reported. Any ongoing SAEs, AESIs, or treatment-related Grade 3/4 AEs will be followed until resolution or stabilization or until loss to follow-up. AEs and laboratory abnormalities will be graded according to the NCI CTCAE grading system (v5.0) and recorded on the eCRF.

If a patient begins subsequent anticancer therapy, the sponsor will terminate collection of SAEs, with the exception of the AESIs of MDS and AML.

Complete details for monitoring AEs, including the definition of drug-related AEs, are provided in Section 8.

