8.6 Pregnancy or Drug Exposure During Pregnancy

Pregnancy is an exclusion criterion. In addition, due to inclusion criteria #4, requiring at least a bilateral salpingo-oophorectomy and partial omentectomy, women of child-bearing potential will not be randomized in this study.

All study participants must avoid pregnancy achieved through assisted reproductive technology, for the duration of study treatment and for a minimum of 6 months following the last dose of study drug (oral or IV, whichever is later).

8.7 Recording of Adverse Events, Serious Adverse Events, and Adverse Events of Special Interest

Events that occur after signing of informed consent but prior to initiation of study drug, unless due to a protocol-mandated procedure, should be recorded on the Medical History eCRF; however, events are to be reported as SAEs if serious and related to a protocol-mandated procedure during this time. Any AE (serious or non-serious) that occurs after first dose of study drug through 28 days after receiving the last dose of oral or IV study drug, whichever occurs later, will be recorded on the AE eCRF. Additionally, only AEs that are related to IV drug that occur between 28 days and 5 months after the last dose of IV drug will be recorded on the AE eCRF.

After the 28-day reporting window following discontinuation of randomized treatment, only SAEs assessed as potentially related to study drug should be reported.

After the 28-day or 5-month reporting window after discontinuation of randomized treatment, AESIs of MDS and AML, irrespective of causality, should be reported.

• AESIs of pneumonitis or similar events should only be reported up to, but not beyond, the SFU1 (28-days after the last dose of rucaparib). After this period, only events considered serious and related to study drug should be reported as SAEs (including serious reports of pneumonitis or similar events, ie, interstitial lung disease, pulmonary fibrosis, acute interstitial pneumonitis, alveolitis necrotizing, alveolitis, hypersensitivity pneumonitis, and organizing pneumonia), if considered to be related to study drug.

Information on the follow-up of AEs, SAEs, and AESIs is provided in Section 8.8.

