9.7.1 Adverse Events

AEs will be classified using the Medical Dictionary for Drug Regulatory Activities (MedDRA) classification system. The severity of the toxicities will be graded according to the NCI CTCAE v5.0 later. Only treatment-emergent adverse events (TEAEs) will be collected: TEAEs are defined as AEs with onset date on or after the date of first dose of study drug until 28 days after the last dose of oral study drug or 5 months after the last dose of IV study drug, whichever occurs later.

The number and percentage of patients who experienced TEAEs for each System Organ Class (SOC) and preferred term will be presented. Multiple instances of the TEAE in each SOC and multiple occurrences of the same preferred term are counted only once per patient. The number and percentage of patients with at least one TEAE will also be summarized.

Separate tables will be presented as follows:

- All TEAEs;
- TEAEs by CTCAE grade;
- Grade 3 or greater TEAEs;
- Treatment-related TEAEs;
- Serious TEAEs;
- TEAEs with an outcome of death;
- TEAEs leading to discontinuation of study drug;

- TEAEs resulting in interruption/delay of study drug; and
- TEAEs resulting in dose reduction of study drug.

The incidence of TEAEs will be summarized by relationship to study drug according to the following categories: "treatment-related," or "not treatment-related". If a patient experiences multiple occurrences of the same AE with different relationship categories, the patient will be counted once, as a relationship category of treatment related.

If a patient experiences multiple occurrences of the same AE with different toxicity grades, the patient will be counted once for the maximum (most severe) toxicity grade. AEs with a missing toxicity grade will be presented in the summary table with a toxicity grade of "Missing." For each toxicity grade, the number and percentage of patients with at least one TEAE of the given grade will be summarized.

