#### 11 SAFETY ANALYSIS

Safety and tolerability is one of the secondary study objectives. Overall safety and tolerability will be measured by the incidence of adverse events, serious adverse events, adverse events leading to discontinuation, deaths, specific laboratory abnormalities (worst grade) and changes from baseline.

The safety analyses will be presented for the safety population presenting the data for each treatment group separately (Arm A [rucaparib and nivolumab], Arm B [rucaparib], Arm C [nivolumab], and Arm D [placebo]). The analyses will be presented by the actual treatment given. Patients randomized to either treatment group containing IV Nivolumab (ie, Arm A or Arm C) who never receive Nivolumab, will be analyzed in the analogous treatment group containing IV Placebo (ie, Arm B or Arm D, respectively).

Summary tables are based on data that are found to be "on-treatment"/ "treatment-emergent" for the oral or IV study drug as outlined in the below sections.

All safety data which is considered treatment-emergent will be summarized. Treatment-emergent is defined as safety data with an onset date on or after the date of first dose of study medication until the date of last dose of oral study drug plus 28 days or date of last IV dose plus 5 months (ie, 152 days), whichever is the latest date.

Descriptive statistics of safety will be presented using the NCI CTCAE v5.0. All AEs, drug-related adverse events, serious adverse events (SAEs) and drug-related SAEs will be tabulated using the worst grade per NCI CTCAE v5.0 by system organ class and preferred term. On-study lab parameters including hematology, coagulation, chemistry, liver function, thyroid, adrenal and renal function will be summarized using worse grade by NCI CTCAE v5.0.

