If a patient experiences multiple occurrences of the same AE with different toxicity grades, the patient will be counted once for the maximum (most severe) toxicity grade. AEs with a missing toxicity grade will be presented in the summary table with a toxicity grade of "Missing." For each toxicity grade, the number and percentage of patients with at least one TEAE of the given maximum grade will be summarized.

The time to the first TEAE and first treatment-related TEAE that results in a dose reduction, delay, interruption, or discontinuation for oral study drug and for IV study drug is defined as 1+ the number of days from the first dose of study drug to the start of the first adverse event. The cumulative incidence is presented in a 1-KM graph for just the patients with an event and the median time to onset will be calculated together with the 95% CI.

Non-TEAEs (pre-treatment and post-treatment) will be presented in the by-patient data listings for the safety population.

MedDRA PTs will be combined for the following similar terms:

- Anaemia or Haemoglobin decreased;
- Asthenia or Fatigue;

Confidential 41 of 52

- ALT or AST increased;
- Neutropenia or Neutrophil count decreased;
- Thrombocytopenia or Platelet count decreased.

In addition, the analysis of combined terms for anemia is explored as a time to first event analysis as described above. Transfusions (blood or plasma) and concomitant medications/growth factor support are provided in patient listings. The number of transfusions and the time to first transfusion will also be summarized.

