If a patient experiences multiple occurrences of the same AE with different toxicity grades, the patient will be counted once for the maximum (most severe) toxicity grade. AEs with a missing toxicity grade will be presented in the summary table with a toxicity grade of "Missing." For each toxicity grade, the number and percentage of patients with at least 1 TEAE of the given maximum grade will be summarized.

The time to the first TEAE of Anaemia or Haemoglobin decreased, and first TEAE leading to a dose reduction, interruption, and/or discontinuation of oral study drug is defined as 1+ the number of days from the first dose of study drug to the start of the first AE. The cumulative incidence is presented in a 1-KM graph for only the patients with an event and the median time to onset will be calculated together with the 95% CI.

Non-TEAEs (pre-treatment and post-treatment) will be presented in the by-patient data listings for the Safety Population.

MedDRA PTs will be combined for the following similar terms:

- Anaemia or Haemoglobin decreased;
- Asthenia or Fatigue;
- ALT or AST increased;
- Neutropenia or Neutrophil Count decreased;
- Thrombocytopenia or Platelet count decreased.

In addition to the cumulative incidence tables of AEs, time adjusted AE summaries for the oral treatment study duration will be created. The time adjusted analyses (ie, 100 patient-treated years) of AEs are defined as the number of total events of a certain AE divided by the patient-years. The patient-years is the total sum of all the years the patients in each treatment arm are treated (ie, from the start of first oral dose to date of last oral dose +1 day). The time adjusted analyses will be summarized for the following:

- 100 patient-treated years for all TEAEs;
- 100 patient-treated years for Grade 3 or greater TEAEs; and
- 100 patient-treated years for serious TEAEs.

In addition, the analysis of combined terms for anemia is explored as a time to first event analysis as described above. Transfusions (blood or plasma) and concomitant medications / growth factor support are provided in patient listings. The number of transfusions is also summarized.

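### MDS and AML are still collected after the treatment-emergent window closes, but neither SAP plans a by-arm safety table that counts those later cases

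*SAP*

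**What the plan says.** **Collection (protocol).** Section 1.1.1.2.3.1 designates MDS and AML as adverse events of special interest. Section 8.7 states that once the 28-day or 5-month reporting window has passed, "AESIs of MDS and AML, irrespective of causality, should be reported". Section 7.4.6 repeats this for long-term follow-up: "AESIs of MDS and AML irrespective of causality, are to be reported as specified in Section 8.7". Section 7.5.4.1 carves these events out when a patient moves to other treatment: "If a patient begins subsequent anticancer therapy, the sponsor will terminate collection of SAEs, with the exception of the AESIs of MDS and AML". Secondary malignancy is monitored every 12 weeks in all patients who have stopped treatment. That monitoring ends at death, loss to follow-up, withdrawal of consent or study closure (Section 7.4.6 and the last footnote to Table 5).

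**Analysis (SAPs).** COMBO SAP Section 11 sets the scope: "All safety data which is considered treatment-emergent will be summarized". Its window runs to the later of last oral dose plus 28 days and last IV dose plus 152 days. MONO SAP Section 11.1 uses last oral dose plus 28 days only. Events outside the window go to listings in both: "Non-TEAEs (pre-treatment and post-treatment) will be presented in the by-patient data listings for the safety population" (COMBO) and "Non-TEAEs (pre-treatment and post-treatment) will be presented in the by-patient data listings for the Safety Population" (MONO).

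**A conflicting sentence.** Protocol Section 9.7.1 says: "Only treatment-emergent adverse events (TEAEs) will be collected". That cannot be squared with Sections 7.4.6, 7.5.4.1 and 8.7.

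**The concern.** The protocol singles out two events for open-ended collection, and the analysis plans then apply the same cut to them as to acute toxicity. A by-patient listing gives neither a denominator nor a rate, and it does not compare arms.

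This matters because safety is a secondary objective. Protocol Section 1.1.1.2.3.1 also says that confounding leaves too little evidence to attribute MDS and AML to rucaparib. A randomized placebo arm with continued follow-up bears directly on that question. Under the SAPs as written, the by-arm adverse event tables would use only part of the data collected to answer it.

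**Working it through.** **Inputs**
- Treatment cap: 24 months after the oral/IV combination starts, which is one 28-day cycle after the first oral dose (Protocol Section 3.1.3).
- Windows: as given above (COMBO SAP Sections 11 and 11.1; MONO SAP Section 11.1).
- First randomization: August 2018 (Protocol Section 9.2.2). MONO cut-off: 23 March 2022 (COMBO SAP Section 2.3).
- One month = 365.25/12 = 30.4375 days.

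**1. The plan's own figure.** 5 × 30.4375 = 152.19, which rounds to the 152 days in the COMBO SAP. Reproduced.

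**2. Window for a patient who completes treatment.** First dose to cap: 28 + 24 × 30.4375 = 758.5 days.
- COMBO: 758.5 + 152 = 910.5 days = 29.9 months.
- MONO: 758.5 + 28 = 786.5 days = 25.8 months.

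This takes both drugs as given up to the cap without delay.

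**3. Window for a patient who stops both drugs at month 12.**
- COMBO: 12 + 152/30.4375 = 17.0 months.
- MONO: 12 + 28/30.4375 = 12.9 months.

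**4. Follow-up available at the MONO cut-off.** From 1 August 2018 to 23 March 2022 is 43.7 months; from 31 August 2018 it is 42.7 months. For the first patients randomized, the time outside the window after full treatment is 43.7 − 25.8 = 17.9 months, or 42.7 − 25.8 = 16.9 months. Patients randomized later have less, and a patient still on treatment at the cut-off has none.

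**5. COMBO.** The documents give no COMBO cut-off date. Assume it falls no earlier than the 16 June 2023 amendment that the COMBO SAP incorporates. The first patients then have at least 57.5 to 58.5 months of potential follow-up, and 57.5 − 29.9 = 27.6 to 58.5 − 29.9 = 28.6 months lie outside the window after full treatment. COMBO SAP Section 7.1 says all patients will be off treatment by the cut-off.

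**6. Is a late case counted anywhere else?**
- The adverse event tables in Section 11.1 of both SAPs are tables of treatment-emergent events. The COMBO sentence about tabulating all AEs by worst grade sits under the treatment-emergent restriction in Section 11.
- The immune-mediated summary (COMBO SAP Section 11.2) uses the same methods as Section 11.1.
- The MONO rates per 100 patient-treated years use treatment-emergent events over time on oral treatment.
- COMBO SAP Section 10.3.10 defers some endpoints to a separate report. MDS and AML are not among them.
- Secondary malignancy appears in both SAPs only in the study design text.
- A fatal case counts as a death in overall survival, without its cause.
- An event whose missing onset date leaves its status undetermined is counted as treatment-emergent in both SAPs.

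**7. A side effect of the two windows.** Arm B is in both comparisons. An Arm B case with onset after last oral dose plus 28 days but by last IV dose plus 152 days is tabulated in COMBO and only listed in MONO.

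**The case against.** **The tables are labelled honestly.** Neither SAP promises an incidence over all follow-up. Both define treatment-emergent events and tabulate those, and late cases are visible in listings, which can be counted by hand if cases are few. This stands as a reason not to call the tables wrong. It does not supply a planned comparison with a denominator.

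**A window tied to treatment is defensible.** Collection continues through subsequent therapy, Protocol Section 1.1.1.2.3.1 names cytotoxic chemotherapy as a confounder, and Section 9.2.2 notes that PARP inhibitor maintenance became standard of care during the trial. A crude count over all follow-up mixes randomized exposure with later treatment. This stands too. It argues for a supplementary table with a caveat, kept beside the treatment-emergent tables.

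**MONO is partly past.** Its primary analysis has been performed and Arms B and D unblinded (COMBO SAP Section 3.5), so any MONO addition is post hoc and must say so.

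**The sentence in Section 9.7.1 may be a slip.** The collection rules elsewhere are consistent, so nothing suggests that data are being lost. It still needs correcting.

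Stronger readings are tempting but not supported:
- A reader might infer that collection is lifelong. It also ends at loss to follow-up, withdrawal or study closure.
- A reader might infer that these events are followed because they appear late. The stated reason is that they have been observed after cytotoxic chemotherapy and with PARP inhibitors.
- A reader might infer that half or more of the cases would be missed. That needs an assumed constant hazard and a long common follow-up. Five years, for example, was impossible at the MONO cut-off.

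**Conclusion.** The point holds for both SAPs. MDS or AML with a known onset after the treatment-emergent window is collected under the protocol but enters no planned between-arm safety table or rate. This follows from a stated rule in each SAP, not from missing detail.

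The size can be given only as time outside the window. After full treatment without delays, the window closes at about 30 months (COMBO) or 26 months (MONO) from first dose. For the first patients randomized, up to about 17 to 18 months of potential follow-up lay outside it at the MONO cut-off. The documents give no MDS/AML rate or onset distribution, so neither the number nor the share of omitted cases can be computed. Nor do they support calling the reported rate falsely low: it is a treatment-emergent rate, presented as such. The change is worth making, and it does not touch the efficacy analyses.

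**What to change.** 1. **COMBO SAP Section 11.1.** Add a supplementary table, by arm in the Safety Population, of MDS and AML and of other secondary malignancies. Count all cases from first dose to data cut-off regardless of the treatment-emergent window. Give the number and percentage of patients, the rate per 100 patient-years of follow-up, and cumulative incidence with death as a competing event. Keep it alongside the treatment-emergent tables.
2. **MONO.** Add the same table to the final overall survival reporting, labelled as added after the primary analysis.
3. **Caveat.** Post-window cases may reflect subsequent therapy. Flag those with onset after it began, and say so in a footnote.
4. **Protocol Section 9.7.1.** Reconcile the statement that only treatment-emergent events are collected with Sections 7.4.6, 7.5.4.1 and 8.7 and the Table 5 footnotes.

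The cost is one more output per comparison from data already collected, plus one corrected protocol sentence. The downside is interpretive: the all-follow-up comparison carries confounding by later treatment, which the flag discloses but does not remove.

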3.1.6 Post-treatment Follow-up Phase

All patients will be followed for at least 5 months after the last IV dose of study treatment. Safety Follow-up Visit 1 (SFU1) should occur 28 days (± 7 days) after last dose of study drug (oral or IV, whichever is later) or can be performed on the date of discontinuation if that date is at least 28 days from the last dose. Assessments will include AEs, physical examination, vital signs and weight measurements, central laboratory hematology, serum chemistry, and CA-125 measurement, ECG, ctDNA analysis (SFU1 only), concomitant medications, ECOG performance status, therapies and procedures, study drug accountability, and PRO. Safety Follow-up Visit 2 (SFU2) should occur approximately 5 months (± 7 days) from the last IV dose of study drug. The same assessments performed at SFU1 will be performed at SFU2; however, chemistry and hematology are only necessary if toxicities are present. If a patient remains on oral study drug after discontinuation of IV study drug, the SFU2 can be performed at the next cycle visit, provided it has been at least 5 months since the last IV dose.

Patients who discontinued treatment for reason other than disease progression or death should continue to have tumor scans performed at 12-week intervals relative to C2D1 (flexibility with scheduling within 1 week prior to planned imaging date is permitted) for the

first 3 years and every 24 weeks thereafter until objective radiological disease progression by RECIST v1.1 is documented, as assessed by the investigator.

An optional tumor biopsy will be collected from patients who experience disease progression/randomized treatment discontinuation and provide appropriate consent.

Patients will also be followed long-term for survival, subsequent treatments, and monitoring for secondary malignancy every 12 weeks (± 14 days) after SFU1 until death, loss to follow-up, withdrawal of consent, or study closure.

If a patient begins subsequent anticancer therapy, the sponsor will terminate collection of SAEs, with the exception of the AESIs of MDS and AML.

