#### 11.1 Adverse Events

AEs will be classified using the MedDRA version 22.0 or higher classification system. The severity of the toxicities will be graded according to the National Cancer Institute Common Terminology Criteria for Adverse Events (NCI CTCAE) v5.0 or later. Treatment-emergent adverse events (TEAEs) are defined as events with an onset date on or after the date of first dose of study medication until the date of the last oral study medication plus 28 days or date of last IV dose plus 5 months (ie, 152 days), whichever is the latest date. Also, AEs will be considered treatment-emergent if all or part of the date of onset of the adverse event is missing and it cannot be determined if the AE meets the definition for treatment-emergent.

The number and percentage of patients who experienced TEAEs for each SOC and PT will be presented. Multiple instances of the TEAE in each SOC and multiple occurrences of the same PT are counted only once per patient. The number and percentage of patients with at least one TEAE will also be summarized.

Separate tables will be presented as follows:

- All TEAEs;
- TEAEs by CTCAE grade;
- Grade 3 or greater TEAEs;
- Treatment-related TEAEs, for oral treatment and IV treatment separately, and also both;
- Serious TEAEs;
- TEAEs with an outcome of death;
- TEAEs leading to discontinuation of study medication for oral treatment and IV treatment separately, and also both;
- TEAEs resulting in reduction oral study medication;
- TEAEs resulting in interruption of oral treatment and IV treatment separately, and also both;
- TEAEs resulting in reduction or interruption of oral treatment;
- Time to the first TEAE that results in a reduction of oral treatment;
- Time to the first TEAE that results in an interruption of oral treatment or IV treatment separately, and also both;
- Time to the first TEAE that results in discontinuation of oral treatment or IV treatment separately, and also both.

The incidence of TEAEs will be summarized by relationship to either oral or IV study drug according to the following categories: "treatment-related," or "not treatment-related". If a patient experiences multiple occurrences of the same AE with different relationship categories, the patient will be counted once, as a relationship category of treatment related.

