#### 11.2 Immune-Mediated Adverse Events

Adverse events that meet the definition of Immune-Mediated AEs will be summarized similarly as described in Section 11.1.

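### ATHENA-COMBO SAP 11.1 leaves MDS/AML arising after the TEAE window to patient listings, so the planned by-arm count omits late cases that the protocol keeps collecting

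*SAP*

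**What the plan says.** **SAP (ATHENA-COMBO).** Section 11 sets the scope of the safety tables: "All safety data which is considered treatment-emergent will be summarized". Sections 11 and 11.1 close the window at the last oral dose plus 28 days or the last IV dose plus 152 days, taking the later date. An event whose onset date is too incomplete to classify counts as treatment-emergent. Apart from transfusion summaries, the tables named in 11.1 are TEAE tables. Within them, "Multiple instances of the TEAE in each SOC and multiple occurrences of the same PT are counted only once per patient". Events outside the window are handled thus: "Non-TEAEs (pre-treatment and post-treatment) will be presented in the by-patient data listings for the safety population". The SAP has no AESI section and does not name MDS or AML. Section 2.2 mentions monitoring for secondary malignancy every 12 weeks, but no analysis of it follows.

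**Protocol.** Section 1.1.1.2.3.1 makes MDS and AML events of special interest. After the 28-day or 5-month window, Section 7.5.4.1 limits reporting to SAEs potentially related to study drug, "and AESIs of MDS and AML irrespective of causality, need to be reported". Section 3.1.6 adds: "If a patient begins subsequent anticancer therapy, the sponsor will terminate collection of SAEs, with the exception of the AESIs of MDS and AML". Section 7.4.6 also provides: "Subsequent treatments, secondary malignancy monitoring, and OS information will be collected for all patients every 12 weeks".

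**The concern.** Collection and analysis do not match. The protocol makes a deliberate exception so that MDS/AML is still captured late and after further therapy, but the SAP's rule for its tables stops at the TEAE window. A late case would be visible in a listing, with no count by arm, no denominator and no time at risk.

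Protocol 1.1.1.2.3.1 says that causality for rucaparib is unresolved because affected patients had confounding risk factors such as earlier cytotoxic chemotherapy. A randomized by-arm count bears directly on that question, and the planned one leaves out the late part of follow-up. What is at stake is a descriptive safety result. No efficacy conclusion depends on it.

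**Working it through.** **1. The plan's own window figure.** Five months in days: 5 × 365.25/12 = 152.19, which agrees with the stated 152.

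**2. Longest possible window.** Cycle 1 is oral only (28 days); treatment is capped at 24 months from Cycle 2 Day 1 (730 days); the IV tail is 152 days. 28 + 730 + 152 = 910 days, or 29.9 months.

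**3. Timing of the primary analysis.** Inputs from SAP 2.4: 400 + 400 patients, 600 events, median PFS 28 months (A) and 20 months (B), 24-month accrual. I assume exponential PFS and uniform accrual. With λ = ln 2/median, PFS averaged over accrual is

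S(T) = [exp(−λ(T − 24)) − exp(−λT)] / (24λ).

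Solving 400(1 − S_A) + 400(1 − S_B) = 600 gives T = 60.3 months, where S_A = 0.307 and S_B = 0.193 (sum 0.500). Potential follow-up runs from 60.3 − 24 = 36.3 to 60.3 months, mean 48.3.

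**4. Time outside the window for a patient treated to the cap and alive at that analysis.**
- Minimum: 36.3 − 29.9 = 6.4 months
- Mean: 48.3 − 29.9 = 18.4 months
- Maximum: 60.3 − 29.9 = 30.4 months

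**5. Mean time inside the window.** Treatment runs to progression or the cap of 758 days (24.9 months), so mean treatment time is (1 − exp(−24.9λ))/λ. Adding the 5.0-month tail, and ignoring deaths and early stopping for toxicity:

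| Arm | Median PFS (months) | Mean treatment (months) | Mean in window (months) |
|---|---|---|---|
| A | 28 | 18.6 | 23.6 |
| B | 20 | 16.7 | 21.7 |
| D | 12 (protocol sample size table) | 13.2 | 18.2 |

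A versus B: 23.6/21.7 = 1.09. No PFS assumption is given for Arm C, so it is not computed.

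**6. Share of all follow-up time outside the window.** Simulation of 1,000,000 patients per arm, with death at progression plus an exponential post-progression time. The documents give no post-progression survival, so its median is an assumption and is varied:

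| Assumed post-progression median | A | B | D |
|---|---|---|---|
| 12 months | 36.9% | 37.3% | 39.6% |
| 24 months | 42.5% | 44.7% | 49.6% |

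The range is therefore about 37% to 50%. If 30% of patients stopped treatment early (an assumption, with the 24-month median), the shares become 49.3%, 51.0% and 55.0%.

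**7. Cross-check on calendar dates.** Protocol 9.2.2 places the first randomization in August 2018 and expects randomization to close in the third quarter of 2020. Taking the end of each period, and a cut-off no earlier than Amendment 5 (16 June 2023), follow-up is 57.5 months for the first patient and 32.5 for the last. Beyond the longest window that leaves 57.5 − 29.9 = 27.6 and 32.5 − 29.9 = 2.6 months.

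**The case against.** Several points on the other side are sound.

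- **Nothing is lost.** Late cases are collected and listed, and cases inside the window appear by preferred term in the TEAE tables. The listing sentence in 11.1 neither names MDS/AML nor excludes a table; the restriction comes from Section 11. That narrows the point to late cases but does not remove it, because no other table is planned.
- **The protocol asks for no such table.** Section 9.7.1 lists none for AESIs and speaks of collecting treatment-emergent events only. A reader might infer a departure from the protocol; there is none. This is a gap in the SAP. Sections 3.1.6, 7.5.4.1 and 8.7 make clear that late MDS/AML is collected.
- **Late cases are confounded by later therapy.** True, and any table should say so.
- **MDS/AML is not unique.** Protocol 7.4.6 also follows secondary malignancies in all patients until death or study closure, so one should not read MDS/AML as the only category followed this way.
- **Unequal exposure is a general feature of treating to progression.** It is modest for A versus B. The gap is wider for B versus D (21.7/18.2 = 1.19), but that is the monotherapy comparison, for which MONO SAP 11.1 already plans rates per 100 patient-treated years for all, Grade 3 or greater, and serious TEAEs.

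A reader might also infer that pneumonitis goes uncounted. The documents do not support that. Protocol 8.7 names pneumonitis and seven similar events, and none is among the five groups introduced by "MedDRA PTs will be combined for the following similar terms", but each still has its own preferred-term row. Section 11.2 may also group some of them: "Adverse events that meet the definition of Immune-Mediated AEs will be summarized similarly as described in Section 11.1". Its definition is not given, and Protocol 5.8 recognises a pulmonary group of immune-related events. A grouped row is a reporting preference.

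**Conclusion.** The point holds for late MDS/AML: the by-arm count planned in the ATHENA-COMBO SAP stops at the TEAE window, while the protocol's collection does not. Its importance is optional.

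About 37% to 50% of follow-up time falls outside the window, and mean in-window time differs between A and B by a factor of about 1.09. These are design projections. They rest on exponential PFS at the planned medians, uniform 24-month accrual, treatment to progression or the cap, and an assumed post-progression median of 12 to 24 months. Early stopping for toxicity would raise the outside share.

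Two stronger readings should be resisted. The percentages are not the proportion of MDS/AML cases missed, because the documents give no incidence or onset times. Shares of 51% (A), 55% (B) and 62% (D) arise only if nobody dies, which does not fit SAP 10.2.2, where the final survival analysis is projected at about 560 deaths.

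**What to change.** In ATHENA-COMBO SAP 11.1, add one descriptive table for Arms A, B, C and D, by actual treatment as in Section 11. Treat MDS/AML as one combined term, count each patient once, and show:

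- (a) onset within the TEAE window;
- (b) onset at any time up to the cut-off, split into before and after the start of subsequent anticancer therapy, and labelled as confounded by that therapy;
- the number of patients and the person-time for both (a) and (b).

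Label the B versus D figures as descriptive, since SAP 3.5 records that the sponsor team was unblinded to those arms on 23 March 2022. Other secondary malignancies, already collected every 12 weeks, can be added as a row.

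A grouped pneumonitis row is optional. If added, it should cover the SAP's full TEAE window and not stop at the 28-day safety visit. One rule in Protocol 8.7 and 8.8 does stop pneumonitis AESI reporting at that visit. But Sections 8.7 and 8.10 also require AESIs, related or not, through 28 days after oral or 5 months after IV dosing, whichever is later. Stopping early could push pneumonitis in the months after nivolumab out of the main row.

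The cost is one table from existing data, with no new collection, no alpha and no change to any efficacy analysis.
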